6.11.2 Sensitivity Analysis of the First Co-Primary Endpoint

Sensitivity analysis may be carried out using the Cochran-Mantel-Haenszel (CMH) test stratified by the randomization stratification factors (baseline TSS [<28 vs. ≥ 28] and Disease Strata [EG \pm EoD vs. EoD]) to assess robustness of the Fisher's exact test results.

A sample SAS code for the pairwise comparison is as follows.

```
* COMPUTES CMH P-VALUE AND NEWCOMBE COMMON RISK DIFFERENCE ;
ods output CMH=PVAL(where=(alhypothesis='Row Mean Scores Differ'));
CommonPdiff=DIFF;
proc freq data=ADEF ;
  tables TSS_STRAT*DISEASE_STRAT*TRTP*RESP / cmh commonriskdiff
  (cl=NEWCOMBE) ;
run ;
```

The rationale for specifying the Fisher's exact test as the primary analysis as opposed to specifying the CMH is because when a stratum has 100% response for 1 treatment group and 0% response for another treatment group, the CMH test may lose efficiency or not be computable. This is evident from the Phase 2 study outcome.

6.11.3 Subgroup Analysis of the First Co-primary Endpoint

Analysis comparing AK002 and placebo will use the Fisher's exact test for each of the subgroups defined in Section 5.9.

6.11.4 Analysis of the Second Co-Primary Endpoint

The second co-primary endpoint will be analyzed by ANCOVA (primary analysis) using the imputed data set (Section 5.4.2). The LS mean, SE, and 95% CI for each treatment group and for the between group difference will be derived from ANCOVA with treatment as factor, baseline PRO TSS (continuous) and disease strata (EG \pm EoD, EoD) as covariates. The hypothesis test for the treatment effect will be carried out by the F-test. The synthesizing method will be used to combine the results from multiple imputations.

6.11.5 Sensitivity Analyses of the Second Co-Primary Endpoint

The two sensitivity analyses planned below are constructed based on the already imputed biweekly data set from Section 5.4.2. From this imputed data set, the biweekly TSS is set to missing if it is derived from the daily scores containing ≥ 4 daily scores collected on/after the ICE. This setting creates the monotone missing data set.

The first sensitivity analysis is based on the placebo-based pattern-mixture model for the missing data imputation under the missing not at random (MNAR) assumption. In this model, subjects

from the active treatment group after the ICE are assumed to behave like the subjects from the placebo group. Their missing data are imputed using the response profile from the placebo subjects who have similar baseline covariates and prior response trajectory. The sample SAS code follows.

```
proc mi seed=135791 n impute=10;
  class TRTMT;
  var B_EOS DISEASE_STRAT B_TSS TSS_W01_02 TSS_W03_04 ...
    TSS_W21_22
    TSS_W23_24;
  monotone reg;
  mnar model (TSS_W01_02 TSS_W03_04 ... TSS_W21_22 TSS_W23_24 /
    modelobs=(TRTMT='0')) ; * CODE 0 IS FOR PLACEBO GROUP ;
run ;
```

The second sensitivity analysis is based on the tipping point method. In this method, the missing biweekly TSS will be imputed with different adjustments for the active treatment subjects and placebo subjects under the MNAR assumption in which the search for a tipping point reverses the study conclusion (i.e., p-value no longer <0.05 for the treatment effect). A shift ranging from $-x$ to $+y$ representing different levels of improvement or worsening due to ICE will be added to the imputed TSS. An example of the SAS code is as follows.

```
proc mi seed=579864 n impute=10;
  class DISEASE_STRAT TRTMT;
  var B_EOS DISEASE_STRAT B_TSS TSS_W01_02 TSS_W03_04 ...
    TSS_W21_22 TSS_W23_24;
  monotone reg;
  mnar adjust (TSS_W01_02 / adjustobs=(TRTMT='1') shift=&d1.)
  adjust (TSS_W03_04 / adjustobs=(TRTMT='1') shift=&d1.)
  ...
  adjust (TSS_W21_22 / adjustobs=(TRTMT='1') shift=&d1.)
  adjust (TSS_W23_24 / adjustobs=(TRTMT='1') shift=&d1.)
  adjust (TSS_W01_02 / adjustobs=(TRTMT='0') shift=&d0.)
  adjust (TSS_W03_04 / adjustobs=(TRTMT='0') shift=&d0.)
  ...
  adjust (TSS_W21_22 / adjustobs=(TRTMT='0') shift=&d0.)
  adjust (TSS_W23_24 / adjustobs=(TRTMT='0') shift=&d0.);
run;
```

Note, a positive adjustment (shift>0) will increase (worsen) TSS and a negative adjustment (shift<0) will reduce (improve) TSS. Varying shift parameter from 0 (minimum) to maximum, where maximum shift parameter will be guided by the mean difference between subjects that drop out after the t^{th} visit and subjects that continue. This sensitivity analysis will vary the shift parameter independently between the active treatment subjects and placebo subjects.

After the data are imputed, the ANCOVA with the synthesizing method will be applied using methods described in Section 5.4.2.

P-values for the between treatment comparison from the synthesized ANCOVA results will be plotted against the shift parameters to demonstrate the robustness of the study conclusion against the various imputation strategies to account for the ICE effect.

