5.4.2 Missing Daily PRO Scores at Weeks 23–24

PRO daily scores will be set to missing if they are collected after subjects have experienced ICE. For the endpoints of change in the weekly average of PRO TSS, when ≥ 4 of 7 daily scores are available, the weekly average score will be calculated using the available daily scores. (See [Appendix 1](#) for justification of allowing weekly average being calculated from ≥ 4 daily scores.) This calculation implies the missing daily scores are the same as the mean of the non-missing daily scores. When ≥ 4 daily scores are missing, the weekly score will be set to missing. For the calculation of the average PRO TSS over Weeks 23-24, if ≥ 1 weekly score is missing, the biweekly average of Weeks 23–24 will be considered missing.

Missing average of Weeks 23–24 TSS will be imputed using the Markov Chain Monte Carlo (MCMC) method. Baseline tissue eosinophil count and PRO TSS, and disease stratum (EG \pm EoD vs. EoD without EG) will be included along with the average biweekly PRO TSS (W01_02, W03_04, W05_06, ..., W21_22, W23_24) in the multivariate distribution construction. The imputation will be carried out for each treatment group separately and will be executed multiple (50) times (MI). The purpose of MI is to account for the imputation variability in the parameter estimates. An example of the SAS code for this imputation follows.

```
proc mi data=TSS seed=1357986420 n impute=50
  out=TSS_IMMPUTED ;
  by TRTMT ;
  class DISEASE_STRAT ;
  mcmc chain=multiple impute=full initial=em nbiter=200 niter=100 ;
  var B_EOS DISEASE_STRAT (3 levels) B_TSS TSS_W01_02 TSS_W03_04
  ... TSS_W21_22 TSS_W23_24 ;
  run ;
```

After the imputation, the least squares mean (LSM) and standard error (SE) are derived from the conventional ANCOVA from each imputed data set.

These LSM and SE are synthesized to derive the imputation variability-adjusted LSM and SE for each treatment group and for the between treatment difference. These synthesized LSM and SE are then used in the hypothesis test for the between treatment difference. An example of the SAS code for the synthesized LSM comparisons between treatment is as follows.

```
ods output ParameterEstimates=LSMDIF ;
proc mianalyze data=DIFF alpha=0.05 ;
  modeleffects LSM ;
  stderr SE ;
run ;
```

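### The tipping-point imputation code for the TSS co-primary leaves treatment out of the model, so its zero-shift point pools the arms and is not the by-arm primary analysis

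*SAP*

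**What the plan says.** SAP 5.4.2 says of the primary imputation: "The imputation will be carried out for each treatment group separately". The code there and in Appendix 4 carries this out with `BY TRTMT`.

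The two sensitivity analyses in SAP 6.11.5 start from that imputed data set and first blank the scores affected by an intercurrent event (ICE): "the biweekly TSS is set to missing if it is derived from the daily scores containing" four or more daily scores from the ICE onward. Protocol 15.6.1 gives their purpose as assessing departures from missing at random (MAR).

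The tipping-point call then has these parts:

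- Class statement: "class DISEASE_STRAT TRTMT".
- Imputation model: "var B_EOS DISEASE_STRAT B_TSS TSS_W01_02 TSS_W03_04", continuing through the later biweekly scores. `TRTMT` is not in the list.
- Shifts, applied window by window and by arm, for example "adjust (TSS_W03_04 / adjustobs=(TRTMT='1') shift=&d1".
- No `BY` statement.

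The shift grid is described as "Varying shift parameter from 0 (minimum) to maximum"; the preceding text allows a range from −x to +y. Both contain zero, and the two arms' shifts vary independently. The p-values are to be "plotted against the shift parameters to demonstrate the robustness of the study conclusion" (Figure 2 in Appendix 3). The text refers back to 5.4.2 only for the ANCOVA and combining step that follow imputation.

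**The concern.** In `PROC MI` with monotone regression, the `VAR` list defines the model from which missing values are drawn. `CLASS` only declares a variable's type, and `ADJUSTOBS` only chooses which records receive a shift. With treatment in neither `VAR` nor `BY`, one regression is fitted to both arms together. Missing AK002 scores are then pulled toward placebo, and missing placebo scores toward AK002.

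A tipping-point plot is read as a distance: how far the missing values must move from the primary assumption before the conclusion changes. That reading needs the (0,0) point to represent no departure. Here (0,0) comes from a different imputation model, so if there is a benefit, part of the distance is used up before any shift is applied. Nothing in the SAP would tell a reader of Figure 2 that this had happened.

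**Working it through.** **1. The plan's own figure.** With 80 per arm, a difference of 7.4 (16.1 − 8.7, Protocol 15.1) and SD 12.5, SE = 12.5 × √(2/80) = 1.976. Then 7.4/1.976 = 3.744, and power = Φ(3.744 − 1.960) = 0.963 (0.961 with the noncentral t). The stated 96% is reproduced and is not in question.

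**2. The three imputation calls side by side.**

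| Call | `BY TRTMT` | `TRTMT` in `VAR` | Model fitted to |
|---|---|---|---|
| Primary (5.4.2, Appendix 4) | yes | not needed | each arm separately |
| Placebo-based (6.11.5) | no | no | placebo only, through "modelobs=(TRTMT='0" |
| Tipping point (6.11.5) | no | no | both arms pooled |

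**3. Why pooling attenuates.** Let Δ be the by-arm difference, π the fraction per arm with post-ICE values, and c the share of Δ that earlier scores carry into the imputed values. As a first approximation:

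zero-shift difference = (1 − π)Δ + πcΔ, so loss = π(1 − c)Δ.

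With Δ = 7.4 and c = 0, the loss is about 0.74, 1.48 and 2.22 points at π = 10%, 20% and 30%. Earlier scores reduce this, more so when the ICE is late.

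**4. Simulation at zero shift.**

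- From the documents: 80 per arm, 12 biweekly scores, mean reductions 16.1 and 8.7, SD of change 12.5, baseline mean 30, and 70 of 160 patients EoD-only.
- Assumed: baseline SD 11; equal ICE rates in the arms; correlation 0.55 + 0.45 × 0.85^lag; effect plateau by Week 8; all windows after the ICE reset.
- Method: monotone regression imputation (20 imputations), ANCOVA on treatment, baseline TSS and stratum, Rubin's rules, 1,000 trials per base scenario.

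Mean loss in points, pooled against by-arm. In brackets is the range over this run and two separately written repeats:

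| ICE timing | 10% ICE | 20% ICE | 30% ICE |
|---|---|---|---|
| Uniform | 0.33 (0.31–0.39) | 0.65 (0.57–0.65) | 0.99 (0.88–0.99) |
| Weeks 1–8 | 0.59 (0.59–0.65) | 1.19 (1.19–1.25) | 1.83 (1.74–1.92) |
| Weeks 21–24 | 0.07 (0.05–0.07) | 0.15 (0.15–0.21) | 0.22 (0.21–0.31) |

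The simulation SE of the main figures is 0.006–0.027. Divided by the c = 0 values in step 3, they give 1 − c of about 0.45 (uniform), 0.8 (early) and 0.1 (late), stable across ICE rates, as the approximation implies. With `TRTMT` in `VAR`, the mean estimate was within 0.08 points of the by-arm result in all 72 scenarios examined.

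**5. Sensitivity of the size.** The 72 scenarios cover four correlation structures and two effect time courses. The loss ranged from 0.07 to 2.30 points (SE up to 0.07). Late ICEs reached 1.22 if the effect was still growing at Week 24. Separate large-sample runs gave zero-shift differences of about 7.2–7.7 by arm or with treatment in the model. The pooled code gave 6.6–7.2, 5.8–7.0 and 5.1–6.6 at 10%, 20% and 30%.

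Read literally, the reset rule blanks only windows that contain post-ICE diaries. If half of ICE subjects have none and keep their by-arm imputation, the losses are 0.18, 0.35, 0.51 (uniform), 0.30, 0.54, 0.94 (early) and 0.04, 0.06, 0.13 (late).

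**6. Effect on p-values.** With all windows reset, the share of significant primary results that are non-significant at zero shift was 0.7%, 1.8%, 3.5% (uniform), 1.8%, 5.4%, 12.3% (early) and at most 0.4% (late). With `TRTMT` in `VAR` it was 0.2–1.4%, which is imputation noise. The uniform 10% figure is therefore within noise and the uniform 20% figure only slightly above it.

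The p-value does not always move in one direction. In four scenarios of 300 trials the pooled p-value exceeded the by-arm one in 62–95% of trials. In another run it was smaller in 16–52%, and some non-significant results became significant.

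**The case against.** The strongest defence is that the code is offered as an example. It names no input or output data set, abbreviates most windows and would need completing before it could run. A reader might infer that the sponsor has decided to pool the arms; the documents do not support that, because no text says so. The point that stands is narrower. The example is the only specification of this imputation model, and the surrounding text does not supply treatment. Under SAP Section 7, derived datasets and tables are programmed twice and must match. Two programmers working from this code would agree on the same omission.

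Second, the consequence is limited. Figure 2 gates nothing under SAP 5.8, and the primary estimate and the placebo-based analysis are reported separately. That is right, and it caps the importance of the point.

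Third, the SAP never states that zero shift must reproduce the primary result; it speaks of robustness to imputation strategies. This softens the point, but Protocol 15.6.1 does define the purpose as departures from MAR, which fixes the natural origin.

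Fourth, the larger losses need 20–30% ICEs, all early and all reset. That is fair: Appendix 2 allows both early and late ICEs, and the documents do not say which will predominate.

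**Conclusion.** The point holds as a specification fault in a sensitivity analysis that should be corrected. Followed as printed, the tipping-point call imputes from a model pooled over arms, so its (0,0) point is not the by-arm MAR analysis. If AK002 is beneficial, the expected zero-shift difference is attenuated. Under uniform ICE times and a 7.4-point effect the loss is about 0.3, 0.65 and 1.0 points at 10%, 20% and 30% ICEs per arm, or 4%, 9% and 13% of the effect (0.33, 0.65 and 0.99 divided by 7.4). It is about 0.6, 1.2 and 1.8 points with early ICEs, about 0.1–0.3 with late ICEs after a plateau, and roughly half as large if half of ICE subjects keep their by-arm values. The reading of the code is firm; these sizes depend on assumed ICE rates, timing and correlations.

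Three stronger readings are not supported:

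- That the fault can only understate robustness. This is true on average; in a single trial the p-value can move either way, largely through imputation noise.
- That the co-primary test is compromised. Its imputation is by arm, and its alpha and power do not depend on 6.11.5.
- That the placebo-based call shares the fault. `MODELOBS` deliberately restricts that model to placebo.

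**What to change.** In the tipping-point call, put `TRTMT` in the `VAR` list before `TSS_W01_02`, for example `VAR TRTMT B_EOS DISEASE_STRAT B_TSS TSS_W01_02 ...`. The position matters: monotone regression predicts each variable from those listed before it, so a treatment term at the end would not enter the score models. Alternatively, run the call separately in each arm with only that arm's `ADJUST` clauses (`&d1.` for AK002, `&d0.` for placebo) and stack the two outputs before the ANCOVA.

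Add a sentence to SAP 6.11.5 saying that the imputation model includes treatment, and that the estimate with both shifts at zero will be reported beside the primary estimate, with any difference beyond Monte Carlo error explained.

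The cost is a line of SAS and one SAP sentence, before unblinding. No data collection, sample size or primary analysis changes.

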Two sensitivity analyses will be conducted to assess the departures from the missing at random (MAR) data assumption. The first sensitivity analysis will be based on the placebo-based pattern mixture model for the missing data imputation under the missing not at random (MNAR) assumption. In this model, subjects from the active treatment group after the ICE events are assumed to behave like the subjects from the placebo group. Their missing data are imputed using the response profile from the placebo subjects who have similar baseline covariates and prior response trajectory. The second sensitivity analysis will be based on the tipping point method. In this method, the missing biweekly TSS will be imputed with different adjustments for the active treatment subjects and placebo subjects under the MNAR assumption in search for a tipping point that reverses the study conclusion (i.e., p-value no longer <0.05 for the treatment effect). Detailed specifications for the analyses outlined above will be provided in the SAP.

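### SAP 6.11.5 gives two incompatible shift ranges for the tipping-point analysis; the second, read literally, omits improved placebo dropouts and can end before a tipping point is reached

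*SAP*

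**What the plan says.** Protocol 15.6.1 describes the second sensitivity analysis of the TSS endpoint as run "in search for a tipping point that reverses the study conclusion" and leaves the detail to the SAP. SAP 6.11.5 repeats that aim and then describes the shift twice.

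- **First description:** "A shift ranging from $-x$ to $+y$ representing different levels of improvement or worsening due to ICE". No value is given for either limit.
- **Second description:** a note after the sample code explains that "a negative adjustment (shift<0) will reduce (improve) TSS", and then gives the range as "Varying shift parameter from 0 (minimum) to maximum". On the upper end, "maximum shift parameter will be guided by the mean difference between subjects that drop out after the" t-th visit and those who continue. No value, step or rule for extending the grid is given.

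The same paragraph adds: "This sensitivity analysis will vary the shift parameter independently between the active treatment subjects and placebo subjects". The sample code has separate shifts for AK002 (d1) and placebo (d0) and applies each at every biweekly visit. P-values are then plotted against the shifts (Figure 2 in SAP Appendix 3) to show how robust the conclusion is.

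**The concern.** A range whose minimum is 0 contains no negative shift, so it cannot be the same range as one that starts at −x. Two programmers could each follow one sentence of 6.11.5 and build different grids.

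The choice matters because higher TSS is worse. The AK002 result is threatened when AK002 dropouts are made worse (d1>0) or placebo dropouts are made better (d0<0). With a minimum of 0 in both arms, d0<0 is never examined, and d0>0 only widens the difference in favour of AK002. The most adverse point left on the grid is d1 at its maximum with d0=0.

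The maximum adds to this. A dropout-versus-continuer difference can be computed only from scores that were observed. The imputation in SAP 5.4.2 already conditions on earlier biweekly TSS. The difference may help in judging what is plausible, but it does not limit how far unseen scores after an intercurrent event (ICE) could lie from their imputed values.

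At stake is the meaning of the robustness statement for a co-primary endpoint. A p-value that stays below 0.05 over a range that leaves out part of the adverse region shows less than the analysis is meant to show.

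**Working it through.** **Inputs.** 80 per arm, difference 7.4, SD 12.5, mean baseline 30 (SAP 3.5). Mean reductions 16.1 and 8.7 (Protocol 15.1). Two-sided 0.05 (SAP 5.8). TSS is the sum of six items scored 0–10, so 0–60 (SAP Table 2). The ICE share m is **assumed**, equal in both arms, from 5% to 30%, because the documents give none. The maximum shift is also assumed.

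**The plan's own figure.** SE = 12.5 × √(2/80) = 1.976. Power for a difference of 7.4 is 96.3% by the normal approximation and 96.1% by the noncentral t with 158 df. The stated 96% reproduces.

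**Room before significance is lost.** 1.96 × 1.976 = 3.87, and 7.4 − 3.87 = 3.53 points.

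**Effect of the shifts, counted once at Weeks 23–24.**

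- Difference: D = 7.4 − m·d1 + m·d0
- Variance in each arm: 12.5² + m(1−m)d²
- SE = √[(v1 + v0)/80]

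Two grids are compared. The signed grid has d1=+s and d0=−s at its worst corner. The zero-minimum grid has d1=+s and d0=0. The smallest s giving p≥0.05 is:

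| m per arm | Signed grid | Zero-minimum grid |
|---|---|---|
| 5% | 30.22 | 54.61 |
| 10% | 16.22 | 30.41 |
| 15% | 11.12 | 21.24 |
| 20% | 8.47 | 16.35 |
| 30% | 5.74 | 11.22 |

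Check at m=10% on the signed grid: D = 7.4 − 0.2 × 16.22 = 4.156; v = 156.25 + 0.09 × 16.22² = 179.9 in each arm; SE = √(2 × 179.9/80) = 2.121; 1.96 × 2.121 = 4.157, so significance is just lost.

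The zero minimum raises the required shift by a factor of about 1.8 (54.61/30.22) to 1.95 (11.22/5.74).

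**Where the two ranges disagree: m=20%, maximum 10.**

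- Zero-minimum: D = 7.4 − 2 = 5.4; v1 = 156.25 + 0.16 × 100 = 172.25; v0 = 156.25; SE = 2.026; z = 2.665; p = 0.008. No tipping point.
- Signed: D = 7.4 − 4 = 3.4; v = 172.25 in each arm; SE = 2.075; z = 1.638; p = 0.10. Tipping point passed.

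**Other cases.**

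- m=20%, maximum 7.4: both grids end short (p=0.003 and p=0.029).
- m=10%, maximum 16.1 (the whole assumed AK002 improvement): the zero-minimum grid ends at p=0.005.
- m=30%, maximum 12.5: even the zero-minimum grid tips (p=0.079).
- Observed difference 5.0, m=20%: the zero-minimum grid tips at about 5.5 points.

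**Carry-forward.** The sample code shifts every biweekly visit. If each shift feeds into the next regression with autocorrelation ρ over k missing visits, the shift at Weeks 23–24 is (1−ρᵏ)/(1−ρ) times nominal. That is 1.75 for ρ=0.5, k=3 and 4.69 for ρ=0.9, k=6. The 16.22 above would then fall to between 16.22/4.69 = 3.5 and 16.22/1.75 = 9.3 nominal points. The SAP does not say which meaning is intended.

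**The case against.** The best defence is that the section can be read sensibly. The sentence before the range defines negative shifts, the first description covers improvement and worsening, and the arms vary independently. On that reading, 0 to maximum is the size of the shift, with its sign set by arm. This is possible, but the SAP does not say so. The fair charge is two conflicting statements, one of which excludes d0<0 if followed as written.

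A reader might also infer that the SAP sets a hard cap. It does not: the maximum is only guided by the observed difference, and the stated aim is to search until the conclusion reverses. What stands is narrower: a maximum is named, it is tied to observed data, and nothing says to go beyond it.

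A reader might further infer that the tipping point lies far outside any likely range, for example by setting a combined two-arm shift of about 3.53/0.10 = 35 points against a one-arm maximum of 3. That comparison mixes two scales, rests on single assumed values and ignores possible carry-forward, so the documents do not support it.

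The other safeguards are real but partial. The placebo-based pattern-mixture analysis tests AK002 patients who behave like placebo after an ICE, but it does not test placebo patients who improve. Figure 2 would show the reader which range was searched, but it cannot show what lies beyond it.

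Finally, failing to tip over a wide, justified range is evidence of robustness. That is correct, and it is the reason for fixing the range in advance.

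**Conclusion.** The concern holds as an inconsistency with a possible consequence. SAP 6.11.5 states two ranges that cannot both apply. Under the second, read literally, improved placebo dropouts are never tested, and the search may end without reaching the tipping point it is meant to find. Whether it does depends on the ICE share, the maximum chosen and the observed effect, none of which the documents give.

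The size is material in the middle of the assumed range: at 20% ICE and a maximum of 10, the choice of sentence decides whether a tipping point is reported. At 5% ICE and the design effect, no maximum examined up to 16.1 tips either grid.

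These figures assume equal ICE shares, the design effect and SD, and a shift counted once at Weeks 23–24. They ignore between-imputation variance and any gain from covariates. The primary analysis and its type I error are unaffected, so this is a low-severity point worth settling before unblinding.

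**What to change.** Before unblinding, replace the second range in SAP 6.11.5 with one signed range per arm. It should include AK002 shifts from 0 upward and placebo shifts from 0 downward, varied independently in a stated step.

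- Extend the grid until p≥0.05 or imputed scores reach the 0–60 TSS limits, and report which came first. The limits can matter: at the planning means, placebo patients average 30 − 8.7 = 21.3 at Weeks 23–24 and so can improve by about 21 points, while AK002 patients average 30 − 16.1 = 13.9 and can worsen by about 46.
- State whether the shift is per visit or the total at Weeks 23–24, and make the code match.
- Report the smallest pairs of shifts that tip the result. Use the dropout-versus-continuer difference only to judge whether those pairs are plausible.

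The cost is a few sentences in the SAP and more grid points. Data collection, sample size and alpha do not change.
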